8.1 Study parameters/endpoints

8.1.1 Main study parameter/endpoint

Descriptive statistics of patient and tumor characteristics, first course treatments, overall survival, and subsequent primary malignancies.

8.1.2 Secondary study parameters/endpoints

1. Time trends in incidence, stage at diagnosis, first course treatments, mortality, and overall survival.
2. Associations between the variables age at diagnosis, sex, race and origin, year of diagnosis, stage at diagnosis, and histologic category (when relevant) with overall survival in multivariable analysis.
3. Standardized incidence of second primary malignancies in patients who survived (i) two or more months, or (ii) five or more years after gastrointestinal cancer diagnosis, relative to the general U.S. population.

8.1.3 Other study parameters (if applicable)

Not applicable.

8.2 Randomization, blinding and treatment allocation

Not applicable

8.3 Study procedures

Study subjects do not undergo any procedures for this study.

8.4 Withdrawal of individual subjects

Not applicable

8.4.1 Specific criteria for withdrawal (if applicable)

Not applicable

8.5 Replacement of individual subjects after withdrawal

Not applicable

8.6 Follow-up of subjects withdrawn from treatment

Not applicable

8.7 Premature termination of the study

Not applicable

9. SAFETY REPORTING**9.1 Temporary halt for reasons of subject safety**

Not applicable

9.2 AEs, SAEs and SUSARs**9.2.1 Adverse events (AEs)**

Not applicable

9.2.2 Serious adverse events (SAEs)

Not applicable

9.2.3 Suspected unexpected serious adverse reactions (SUSARs)

Not applicable

9.3 Annual safety report

Not applicable

9.4 Follow-up of adverse events

Not applicable

10. STATISTICAL ANALYSIS

Analyses are restricted to the first primary gastrointestinal malignancy of included patients. Subsequent primary malignancies diagnosed among patients from the study cohort, including subsequent primary gastrointestinal malignancies, are described separately. Included patients must have a primary gastrointestinal malignancy as their first primary cancer (see Chapter 4.2: inclusion criteria). As a consequence of these decisions, not all (patients with) gastrointestinal malignancies during childhood or adolescence registered in the SEER 17 database are analyzed, which affects the results of our study. For example, calculated incidence rates of the different gastrointestinal malignancies may be slightly underestimated. However, these decisions were deliberately made to facilitate easy interpretation of the study cohort and corresponding data. For example, patients with a diagnosis of a non-gastrointestinal cancer prior to the diagnosis of a primary gastrointestinal cancer during childhood or adolescence represent a small but special group of patients, whose clinical characteristics, treatments and outcomes may be different from children and adolescents with a primary gastrointestinal malignancy as their first primary cancer – the population of interest. To gain insight in the degree of underestimation of incidence rates, additional analyses of all primary gastrointestinal malignancies registered among children and adolescents in the SEER 17 database may be performed.

For analyses that include histologic subgroups or grade data (Table 3), only cases that are microscopically confirmed are analyzed. For analyses including data regarding tumor characteristics (except primary site), treatment, survival, and/or subsequent primary malignancies, cases diagnosed with primary gastrointestinal cancers at autopsy and cases with this diagnosis based on death certificate only are excluded.

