4.2 Inclusion criteria

In order to be eligible for this study, a case must meet all of the following criteria:

- Age (at primary gastrointestinal cancer diagnosis) <25 years
- Diagnosis of a primary gastrointestinal malignancy as an individual's first primary malignancy, based on:
 - Primary site "digestive organs" (ICD-O-3 topography codes C015-C026)
 - Behavior code "malignant" (ICD-O-3 behavior code 3)

Selection of only those cases with a primary gastrointestinal malignancy as their first primary malignancy is done by setting the Multiple Primary Selection option on the Selection tab of SEER*Stat software to First Malignant Primary Only (Non-reported Assumed Malignant).

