10.2 Secondary study parameter(s)

Data will be presented quantitatively (numerically); stratified by age group (<18; 18-24 years at diagnosis).

Age-adjusted incidence and mortality rates are calculated as the average annual number of cases or deaths per million person-years at risk, respectively. For mortality rates, calendar year and age (<18; 18-24 years) represent year and age at death, respectively. Incidence rates of the common gastrointestinal malignancies are based on SEER 17 incidence data (2000-2019); mortality rates of malignant neoplasms of the digestive organs (ICD-O-3 topography codes C015-C026) are based on mortality data of the total U.S. population (1969-2019). In addition, incidence-based mortality (IBM) rates – for cases registered in SEER 17 – may be calculated to partition mortality by digestive cancer subtype (BL, UESL, NEN, HCC, HB, GC, and CRC)³³. The annual population size is obtained from the Census Bureau. Rates are age-standardized using the age structure of the 2000 U.S. standard population. Rates are calculated using SEER*Stat software and plotted using 3-year moving averages³⁴. When 3-year moving averages vary greatly, rates may be plotted using 5- or 7-year moving averages. Trends over time in incidence and mortality are analyzed by Poisson regression, with the calendar year as a continuous regressor variable. In addition, trends over time may be evaluated by linear regression modelling – a method frequently used in prior studies^{34,35} – to allow easier comparisons between studies, as well as with Jointpoint regression modelling to identify change points in the trends. Results are reported as average annual percent changes (AAPC) along with 95% confidence intervals and *P* values.

Trends over time in stage at diagnosis or first course treatments of patients with common GI malignancies are tested with logistic regression, with year of diagnosis as a continuous variable³⁴. The proportions of each stage at diagnosis or treatment category are plotted as weighted 3-year moving averages in percentages. When weighted 3-year moving averages vary greatly, results may be plotted using weighted 5- or 7-year moving averages.

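### Incidence rates inherit the first-primary restriction over a whole-population denominator, and the all-primaries analysis that would measure the shortfall is left optional

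*Combined protocol and SAP*

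**What the plan says.** Section 4.2 (Inclusion criteria) selects only patients whose GI malignancy is their first primary malignancy, through the SEER*Stat multiple-primary setting. Section 10 (Statistical analysis) extends this to the analyses: "Analyses are restricted to the first primary gastrointestinal malignancy of included patients".

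Section 10 also discloses a consequence: "calculated incidence rates of the different gastrointestinal malignancies may be slightly underestimated". It defends the choice: "these decisions were deliberately made to facilitate easy interpretation of the study cohort and corresponding data". As an example it says that patients with a non-GI cancer before their GI cancer "represent a small but special group of patients, whose clinical characteristics, treatments and outcomes may be different" from those of the population of interest. On measuring the shortfall it says only that "additional analyses of all primary gastrointestinal malignancies registered among children and adolescents in the SEER 17 database may be performed".

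Section 10.2 (Secondary study parameters) names SEER 17, 2000-2019, as the source of the incidence rates for the common GI malignancies and sets no separate case selection for them. On the denominator it says: "The annual population size is obtained from the Census Bureau". Trends are fitted by Poisson regression on calendar year and reported as average annual percent changes. Time trends in incidence form part of the first secondary objective (section 2).

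**The concern.** A restriction chosen for a clinical cohort has been carried into the numerator of a population rate. The example given for it, that excluded patients may differ in presentation, treatment and outcome, is a sound reason to keep them out of the survival, treatment and prognostic analyses. It is not a reason to leave their tumours out of a rate whose denominator, as described, still contains people with an earlier cancer.

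Sections 2 and 10.2 refer to incidence without a first-primary qualifier, so a reader who meets a published rate on its own would probably take it as covering all GI malignancies. Such a reader would see a level that is somewhat low by an unreported amount. The amount also need not be the same for every rate. Section 1 says that genetic predisposition, including in young people with colorectal cancer, and some treatments raise second-cancer risk. It is a reasonable inference, though not a figure in the documents, that the excluded share differs by cancer type and between ages under 18 and 18-24.

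**Working it through.** The plan states no rate, case count or size of underestimation, so there is no figure to reproduce. The calculations below are illustrations, and every value of f and N is an assumption.

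**Inputs from the documents.** Numerator: first malignant primaries only (sections 4.2 and 10). Denominator: Census population (section 10.2). Period: 2000-2019, which is 20 calendar years and 19 yearly steps. Trend model: Poisson regression with calendar year as a continuous variable (section 10.2).

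**Level.** Let f be the share of GI primaries under age 25 that are not the person's first malignancy, weighted as the age-standardised rate weights them. With the same denominator:

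first-primary rate / all-primaries rate = 1 - f, so the all-primaries rate is higher by 1/(1 - f) - 1.

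| Assumed f | First-primary rate low by | All-primaries rate higher by |
|---|---|---|
| 0.5% | 0.5% | 0.5% |
| 1% | 1% | 1.0% |
| 2% | 2% | 2.0% |
| 3% | 3% | 3.1% |
| 5% | 5% | 5.3% |
| 10% | 10% | 11.1% |

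The direction holds for any f above zero. The plan calls the patients with an earlier non-GI cancer a small group, which points to the lower rows.

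**Trend.** If the share moves from f0 in 2000 to f1 in 2019:

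shift in annual percent change = exp( ln[(1 - f1)/(1 - f0)] / 19 ) - 1.

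| f0 to f1 | Shift (points per year) |
|---|---|
| 2% to 2% | 0 |
| 1% to 3% | -0.11 |
| 2% to 5% | -0.16 |
| 5% to 10% | -0.28 |
| 3% to 1% | +0.11 |

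For example, 2% to 5% gives ln(0.95/0.98)/19 = -0.00164, or -0.16 points per year. A constant share gives no shift, and a falling share reverses the sign.

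**Precision for comparison.** For N cases spread evenly over 20 years, the variance of calendar year is (20² - 1)/12 = 33.25, and the standard error of the log slope is 1/sqrt(33.25 N). The 95% half-width is 1.96 times that.

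| Assumed N | 95% half-width (points per year) |
|---|---|
| 50 | 4.8 |
| 200 | 2.4 |
| 500 | 1.5 |
| 1000 | 1.1 |
| 2000 | 0.8 |

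The largest assumed shift against the narrowest interval is 0.284/0.76 = 0.37 of a half-width. A 2% to 5% drift with 200 cases is 0.164/2.404 = 0.07 of one.

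**The case against.** The plan has already been open about this. Section 10 states the restriction, says which way it moves incidence, gives a reason and names the analysis that would measure it. First-primary incidence is a legitimate target, and section 10 calls these patients the population of interest. The stated reason is also wider than clinical features: one case set across all analyses is easier to interpret. All of this stands, and it keeps the point small. What it does not answer is why the check should be optional, or why section 10.2 does not label the rates as first-primary.

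A reader might go further in three ways that the documents do not support:

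- **That the first-primary rates are wrong and the all-primaries rates correct.** They answer different questions. The first-primary rate is low only when read as the incidence of all GI malignancies, and the plan's own words are that it may be slightly so.
- **That the incidence trend is biased downward.** Nothing in the documents shows that the excluded share changed over 2000-2019.
- **That the restriction makes incidence and mortality incomparable.** Section 10.2 states no first-primary restriction for mortality, but the two series already differ in geography (SEER 17 against the total U.S.), period (2000-2019 against 1969-2019), site grouping (seven cancers against all digestive organs) and age basis (diagnosis against death). The plan proposes no direct comparison of the two, and lifting the restriction would not make them comparable.

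**Conclusion.** The point holds as a minor one about commitment and labelling. The first-primary rates, read as GI cancer incidence, are low by exactly the excluded share, and the plan does not commit to measuring that share. The direction follows from the case definition and the denominator alone. The size is unknown: 0.5% to 10% is an assumed range, and the upper end sits poorly with the plan's description of the group as small.

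An effect on trends is conditional on a changing share. Even then, the assumed drifts move the annual percent change by about 0.1 to 0.3 points, within the sampling error expected for 50 to 2000 cases. The case for change rests on the level and on how the rates are labelled, not on the trend. The cohort analyses are unaffected.

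**What to change.** In section 10, turn the optional all-primaries analysis into a commitment by replacing 'may be' with 'are'. In section 10.2, report all-primaries incidence rates and trends for ages under 18 and 18-24 beside the first-primary ones, and label each rate with its case definition. Keep First Malignant Primary Only for all cohort analyses.

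The cost is one further SEER*Stat selection, a second set of rates and a footnote. There is a small downside. All-primaries rates count tumours rather than persons, so a second GI primary in the same person counts again, and the totals will not equal the cohort size. The footnote should reconcile the counts, showing separately the GI cancers that followed a non-GI cancer and the further GI primaries in the same person.

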10.1 Primary study parameter(s)

Data is presented quantitatively (numerically). Continuous variables are summarized with medians and ranges, and categorical variables are summarized with frequencies and proportions. Age at diagnosis can also be summarized with frequencies and proportions, using 1-year age categories. Overall survival (OS) is estimated by the Kaplan-Meier method. OS is defined as the time from the date of

diagnosis until the date of death from any cause (event) or until the date of last follow-up. Survival curves may be compared with the log-rank test. Median follow-up is estimated using the reverse Kaplan-Meier method³².

The following descriptive statistics are minimally obtained:

Frequencies and proportions of the different gastrointestinal malignancies – specified in Table 2 – by age group (<18; 18-24 years at diagnosis) and by 1-year age categories (0-24 years). Age distributions of patients diagnosed with common gastrointestinal malignancies (BL, UESL, NEN, HCC, HB, GC, and CRC).

Stratified by age group (<18; 18-24 years at diagnosis):

Frequencies and proportions of the different gastrointestinal malignancies by primary anatomic site (ICD-O-3 topography codes C015-C026). Summarized sex and race and origin data of patients diagnosed with common gastrointestinal malignancies. Frequencies and proportions of surgery, radiation, and chemotherapy as part of the first course of treatment of patients with common gastrointestinal malignancies. Frequencies and proportions of different stages at diagnosis, different grades, and different histologic subtypes of patients diagnosed with CRC. Frequencies and proportions of CRC cases by primary anatomic site (ICD-O-3 topography codes C018.0-C018.9, C019.9, and C020.9). Kaplan-Meier curves depicting OS of patients diagnosed with common gastrointestinal malignancies. Estimated 1- and 5-year OS (with 95% confidence intervals) of patients diagnosed with common gastrointestinal malignancies. Kaplan-Meier curves depicting OS of CRC patients by i) stage at diagnosis, ii) by grade, and iii) by histologic subtype. Frequencies and proportions of patients with multiple primary cancers registered in 2000-2019 by common cancer subgroup (Table 3). Median total number of in situ/malignant tumors of patients diagnosed with common gastrointestinal malignancies.

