DSMB	Data Safety Monitoring Board
EU	European Union
EudraCT	European drug regulatory affairs Clinical Trials
GCP	Good Clinical Practice
GDPR	General Data Protection Regulation; in Dutch: Algemene Verordening Gegevensbescherming (AVG)
IB	Investigator's Brochure
IC	Informed Consent
IMP	Investigational Medicinal Product
IMPD	Investigational Medicinal Product Dossier
METC	Medical research ethics committee (MREC); in Dutch: medisch-ethische toetsingscommissie (METC)
(S)AE	(Serious) Adverse Event
SPC	Summary of Product Characteristics; in Dutch: officiële productinformatie IB1-tekst
Sponsor	The sponsor is the party that commissions the organisation or performance of the research, for example a pharmaceutical company, academic hospital, scientific organisation or investigator. A party that provides funding for a study but does not commission it is not regarded as the sponsor, but referred to as a subsidising party.
SUSAR	Suspected Unexpected Serious Adverse Reaction

- UAVG** Dutch Act on Implementation of the General Data Protection Regulation; in Dutch: Uitvoeringswet AVG
- WMO** Medical Research Involving Human Subjects Act; in Dutch: Wet Medisch-wetenschappelijk Onderzoek met Mensen

SUMMARY

Rationale: Gastrointestinal malignancies are rare in children and adolescents. Consequently, data on clinical features, treatments and outcomes of these patients are limited.

Objective: We aim to describe the patient and tumor characteristics, treatments, and outcomes of children and adolescents diagnosed with primary gastrointestinal malignancies, and to analyze these data for trends over time. In addition, we want to explore independent prognostic factors for overall survival. Finally, we want to describe subsequent primary malignancies diagnosed among patients from the study cohort, as well as to calculate their risk of developing a second primary cancer relative to the general population. Data on children (aged 0-17 years at diagnosis) and young people aged 18-24 years at diagnosis are analyzed separately. Special focus is laid on patients with primary carcinomas of the gastrointestinal tract; particularly colorectal carcinoma.

Study design: This is an observational population-based cohort study based on the publicly available Surveillance, Epidemiology, and End Results (SEER) database.

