Seven common gastrointestinal cancers are specifically distinguished: Burkitt lymphoma (BL), undifferentiated embryonal sarcoma of the liver (UESL), neuroendocrine neoplasms (NEN), hepatoblastoma (HB), hepatocellular carcinoma (HCC), gastric carcinoma (GC), and colorectal carcinoma (CRC). These cancers are depicted in **blue** in Table 2. Subgroup analyses of patients with these malignancies are performed, with a special focus on patients with CRC.

For some of these common cancers, different histologic subtypes are distinguished (Table 3). Grading is based on ICD-O-3 and categorized as 1) Well differentiated, Grade I; 2) Moderately differentiated, Grade II; 3) Poorly differentiated, Grade III; 4) Undifferentiated or anaplastic, Grade IV. Stage at diagnosis is categorized into localized, regional, or distant according to the SEER Summary Staging system (<https://training.seer.cancer.gov/staging/systems/summary/>) by using the Combined Summary Stage variable (available for cases diagnosed between 2004-2019) or the Summary Stage 2000 variable (available for cases diagnosed between 2000-2003). In addition, the Ann Arbor classification is available for staging BL (for cases diagnosed between 2000-2015), and American Joint Committee on Cancer (AJCC) staging schemes are available for NEN, HCC, GC and CRC (Table 3). In any publications of analyses involving staging data, it is clearly stated that different staging schemes were used to stage cancers diagnosed in different years (e.g. AJCC 3rd edition for CRC diagnosed in 2000, and AJCC 8th edition for CRC diagnosed in 2019) – thereby acknowledging the limitations associated with these analyses.

Regarding the first course of treatment, surgery of the primary site, radiation and chemotherapy are dichotomously captured as "yes" or "no/unknown". Similarly, total hepatectomy with liver transplant is specified as "yes" or "no/unknown" for patients with primary hepatic malignancies – including UESL, HB, and HCC (Table 3). In any publications of analyses involving treatment data, the limitations of these data items are acknowledged, as outlined on the SEER website (<https://seer.cancer.gov/data-software/documentation/seerstat/nov2021/treatment-limitations-nov2021.html>).

Table 3. Categorization of data items analyzed for common cancer subtypes

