Subtype	Primary site classification subgroups	Additional staging scheme subgroups	Grading scheme subgroups	Histologic classification subgroups	Surgery primary site (RX Summ--Surg Prim Site (1998+) variable)	Total hepatectomy with transplant (RX Summ--Surg Prim Site (1998+) variable)	Radiation (Radiation recode variable)	Chemotherapy (Chemotherapy recode (yes, no/unk) variable)
BL	ICD-O-3 C015-C026	Ann Arbor stage I-IV	NR	NR	Yes (values 10-90); No or unknown (values 0 and 99)	NR	Yes (all subtypes); No or unknown (incl. "refused" and "recommended, unknown if administered")	Yes; No or unknown
UESL	NR	N/A	NR	NR	Yes (values 10-90); No or unknown (values 0 and 99)	Yes (values 61 and 75); No or unknown (other values)	Yes (all subtypes); No or unknown (incl. "refused" and "recommended, unknown if administered")	Yes; No or unknown
NEN	ICD-O-3 C015-C017, C018.1 (appendix), C018 excl. C018.1, C019-C026	AJCC stage I-IV	ICD-O-3 Grade I-III	Rare Cancer Classification Cat. 1: 230-231 (well differentiated) vs. Cat. 2: 232-233 (poorly differentiated & MiNEN)	Yes (values 10-90); No or unknown (values 0 and 99)	NR	Yes (all subtypes); No or unknown (incl. "refused" and "recommended, unknown if administered")	Yes; No or unknown
HB	NR	N/A	ICD-O-3 Grade I-IV	NR	Yes (values 10-90); No or unknown (values 0 and 99)	Yes (values 61 and 75); No or unknown (other values)	Yes (all subtypes); No or unknown (incl. "refused" and "recommended, unknown if administered")	Yes; No or unknown
HCC	NR	AJCC stage I-IV	ICD-O-3 Grade I-IV	Rare Cancer Classification Cat. 1: 52 (HCC, NOS) vs. Cat. 2: 53 (HCC, fibrolamellar)	Yes (values 10-90); No or unknown (values 0 and 99)	Yes (values 61 and 75); No or unknown (other values)	Yes (all subtypes); No or unknown (incl. "refused" and "recommended, unknown if administered")	Yes; No or unknown
GC	ICD-O-3 C016.0-C016.9	AJCC stage I-IV	ICD-O-3 Grade I-IV	ICD-O-3 Cat. 1: 8140 (AC, NOS), Cat. 2: 8210 + 8220 + 8221 + 8261 + 8263 (AC in polyp/adenoma), Cat. 3: 8480-8482 (MAC), Cat. 4: 8490 (SRCC), Cat. 5: remaining cases (others/unknown) ¹⁶	Yes (values 10-90); No or unknown (values 0 and 99)	NR	Yes (all subtypes); No or unknown (incl. "refused" and "recommended, unknown if administered")	Yes; No or unknown

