CRC	ICD-O-3 C018.0-C018.9, C019.9, C020.9	AJCC stage I-IV	ICD-O-3 Grade I-IV	ICD-O-3 Cat. 1: 8140 (AC, NOS), Cat. 2: 8210 + 8220 + 8221 + 8261 + 8263 (AC in polyp/adenoma), Cat. 3: 8480-8482 (MAC), Cat. 4: 8490 (SRCC), Cat. 5: remaining cases (others/unknown) ¹⁶	Yes (values 10-90); No or unknown (values 0 and 99)	NR	Yes (all subtypes); No or unknown (incl. "refused" and "recommended, unknown if administered")	Yes; No or unknown

New abbreviations: NR, not relevant; N/A, not available; Cat, category; AC, adenocarcinoma; MAC, mucinous adenocarcinoma; SRCC, signet ring cell carcinoma.

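### Must the colorectal carcinoma results be repeated without the appendix (C018.1), which the listed site codes include?

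*Combined protocol and SAP*

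**What the plan says.** The Summary states that "Special focus is laid on patients with primary carcinomas of the gastrointestinal tract; particularly colorectal carcinoma". Section 8 (Methods) repeats the emphasis: "Subgroup analyses of patients with these malignancies are performed, with a special focus on patients with CRC".

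The CRC row of Table 3 gives the sites as "ICD-O-3 C018.0-C018.9, C019.9, C020.9", in the column headed "Primary site classification subgroups". Section 10.1 uses the same range for a required table, split at age 18: "Frequencies and proportions of CRC cases by primary anatomic site (ICD-O-3 topography codes C018.0-C018.9, C019.9, and C020.9"). In the NEN row of Table 3 the same column reads, in part, "C018.1 (appendix), C018 excl. C018.1".

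The Section 10.1 list is a floor: "The following descriptive statistics are minimally obtained". Section 10.2 then plans incidence, stage, treatment and survival trends, a multivariable Cox model and standardized incidence ratios (SIRs) for each common cancer, with CRC as one group. Section 10 also leaves room for extra work on another selection choice, the restriction to first primaries: "additional analyses of all primary gastrointestinal malignancies registered among children and adolescents in the SEER 17 database may be performed".

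**The concern.** The plan names C018.1 as the appendix and sets it apart for neuroendocrine neoplasms, yet the CRC range runs straight through it. That looks like a distinction drawn for one tumour and forgotten for another. CRC is the declared focus, and a reader may take its results to describe colon and rectum alone.

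If appendiceal carcinomas were numerous and had a different stage mix, histology or prognosis, the pooled survival, hazard ratios and incidence trend would partly reflect them. The site table would show how many there are, but not whether the other results hold without them. Because "Primary Site - labeled" is already among the retrieved items in Table 1, a repeat analysis without C018.1 seems an easy safeguard.

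**Working it through.** The plan states no figure on this point that could be reproduced. The check is a count of codes and outputs, a comparison of the two Table 3 rows, and an illustration of scale.

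**1. Codes.** C018.0 to C018.9 is 10 codes. Adding C019.9 and C020.9 gives 10 + 1 + 1 = 12. C018.1 is one of them, and removing it leaves 11. The factual premise is right.

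**2. Outputs.** The minimum list in Section 10.1 has 2 items before the stratification line and 10 after it, so 12. One of these, CRC by subsite code, shows C018.1. Section 10.2 fixes 8 outputs covering CRC: incidence trend, stage trend, treatment trend, survival trend, 1- and 5-year survival by period, the Cox model, and SIRs from two months and from five years. None shows C018.1. Hence 12 + 8 = 20, and 20 − 1 = 19 do not separate the appendix.

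**3. What that count means.** Put any other C018 subsite code in place of C018.1 and the result is again 19 of 20. For C019.9 or C020.9 it is 18 of 20, because the general site table by C015-C026 also separates those codes. The count therefore describes an analysis of CRC as a single group and says nothing particular to the appendix.

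**4. The two rows of Table 3.** The NEN row mostly uses whole-site codes (C015-C017, C019-C026). At that level the appendix disappears into C018 unless it is named, so it is named. The CRC row is written at subsite level, where C018.1 is already a category of its own. The rows differ in coding detail, not in whether the appendix is recognised. NEN is also a separate cancer group in Section 8, so appendiceal NENs are not among the CRC cases. Only other appendiceal carcinomas are at issue.

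**5. Scale, by assumption only.** Let *f* be the appendix share of CRC cases and *d* the appendix 5-year survival minus that of the other sites, *S*. Pooled survival is (1 − *f*)*S* + *f*(*S* + *d*) = *S* + *fd*, so the shift is *f* × *d*. This is exact with complete follow-up and approximate for Kaplan-Meier estimates.

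| Assumed *f* | Shift for *d* = 10 points | Shift for *d* = 30 points |
|---|---|---|
| 2% | 0.2 points | 0.6 points |
| 5% | 0.5 points | 1.5 points |
| 10% | 1.0 points | 3.0 points |
| 20% | 2.0 points | 6.0 points |
| 30% | 3.0 points | 9.0 points |

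If appendix survival is lower, the sign reverses. The documents give neither *f* nor *d*, so no row is preferred. Even a large shift would be a property of the group as listed, not an error in estimating its survival.

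**6. Yield of the rerun.** The CRC column of Table 4 has age 1 + sex 1 + race and origin 3 + year 1 + stage 3 + histology 4 = 13 coefficients, taking age and year as single linear terms. Section 10.2 calls for stratification by age group. Refitting this on fewer cases may be too imprecise to report, especially under 18.

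**The case for a change.** The strongest argument concerns the Cox model. Histologic category is a covariate and primary site is not. If the histology mix differs by site, the CRC histology hazard ratios would carry part of a site effect, and no planned output would reveal it. Section 10 also shows that the investigators accept additional analyses to gauge the effect of a selection rule, so the same could be asked here.

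Part of this stands. The plan cannot separate appendix from histology in that model, and a sensitivity analysis would be feasible with data already retrieved. But the argument applies to every subsite within CRC. The hazard ratios are also presented as exploratory associations within the listed group, already adjusted for stage. Nothing in the documents says that appendiceal carcinoma differs in stage, histology or outcome.

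The parallel with Section 10 is loose. There the plan itself identifies a bias and its direction, namely incidence rates slightly too low, and even then the extra analysis is optional. Here neither a bias nor a direction is known.

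The other reservation is Table 2, which specifies the malignancies. Only its legend is legible in the copy reviewed. If its body excludes the appendix from CRC, the code ranges in Table 3 and Section 10.1 would need to be brought into line with it. That would be a wording matter needing no rerun, and text lost in this copy cannot count against the plan.

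**Conclusion.** There is no defect. Including C018.1 is a definitional choice that the plan states twice and makes visible in a required table by age group. For the CRC group so listed, the planned descriptive, survival, trend and SIR results answer the questions they set. The 19-of-20 count is correct, but it reflects pooled analysis and is no measure of bias. Size and direction of any difference from a colon-and-rectum-only analysis cannot be derived from the documents.

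This rests on two assumptions: that Table 2 does not contradict the code ranges in Table 3 and Section 10.1, and that publications describe CRC by the range the plan gives. A single line saying whether CRC includes the appendix would help readers. A rerun without it is a matter of preference that would change no planned result, and the Section 10.1 list, being a minimum, already leaves room for it if the site table shows enough appendix cases.
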